8.8. Definition of End of Study

The end of study will be the date of the last 6-month telephone follow-up.

9. INTERVENTION: AF ablation

As current practice in our centre, all AF ablations will be performed under general anaesthesia and on uninterrupted therapeutic anticoagulation with warfarin (target INR 2-3 in the last 3 weeks at least) or one of the new non-Vitamin K anticoagulant drugs. A heparin infusion will also be administered during the procedure, with target Activated Clotting Time (ACT) values of 300-350 sec. Fluoroscopy and tri-dimensional electroanatomical mapping will be used by the operator, as usual, as anatomical guide during the procedure.

The procedure critical steps can be detailed as follow:

- *General anaesthesia and TOE.* After general anaesthesia and oro-tracheal intubation, a trans-oesophageal echocardiogram (TOE) will be performed to rule out the presence of thrombus in the LA appendage.

- *Vascular access, coronary sinus catheter placement and LA access.* Venous femoral access will be achieved and a deflectable decapolar diagnostic catheter placed to the coronary sinus. One or two atrial trans-septal punctures will be performed under TOE-guidance. The choice of the trans-septal kit (needle and sheath) and of the number of performed trans-septal punctures will be left to the operator.

- *Luminal oesophageal temperature monitoring.* After the trans-septal puncture(s), the TOE probe will be taken out. A two-plane sinusoidal oesophageal temperature probe, CIRCA's S-Cath (CIRCA, Englewood, CO) will be placed orally to the oesophagus and advanced to the level of the LA. It will be connected to a dedicated CIRCA Temperature Monitor (CIRCA, Englewood, CO), displaying graphically and numerically temperature data from all 12 sensors, updated 20 times per second. Any luminal oesophageal temperature rise $\geq 39^{\circ}\text{C}$ will result in a temperature alert and cessation of RF delivery at that site.

- *LA geometry.* The LA geometry will be reconstructed using the EnSite Velocity mapping system (SJ Medical, St Paul, MN, USA) and an Optima mapping catheter (SJ Medical, St Paul, MN, USA).

- *LA ablation strategy and technique.* The PVs will be encircled in pairs to isolation using an irrigated-tip ablation catheter TactiCath Quartz (SJ Medical, St Paul, MN, USA) via an Agilis deflectable sheath. A point-by-point ablation technique will be used, with a minimum CF of 10 g and a target CF of 20 g for each RF lesion. As current practice, the circumferential ablation line around the PV pairs will be predefined on the electroanatomical LA map, at 1-2 cm from PV ostia with individual adjustments in order to avoid RF delivery in close proximity of the oesophageal probe.

- *RF settings on the LA anterior wall, roof and floor.* As current practice in our centre, an RF power of 40 W will be used on LA anterior wall, roof and floor. The RF application time will be dictated by the achievement of the target FTI and LSI (FTI \geq 400 gs; LSI \geq 6 on LA anterior wall and LSI \geq 5.5 on LA roof and floor).

- *RF settings on the LA posterior wall.* Different RF settings will be used during RF ablation on LA posterior wall, according to randomization group:

- ✓ *Group 1:* 20 W RF power, with target LSI = 4;
- ✓ *Group 2:* 40 W RF power, with target LSI = 4;
- ✓ *Group 3:* 20 W RF power, with and target LSI = 5;
- ✓ *Group 4:* 40 W RF power, with target LSI = 5.

Regardless of the LSI achieved, RF delivery on the LA posterior wall will be promptly terminated in case of any oesophageal temperature rise \geq 39°C or after 60 seconds of continuous RF delivery. The ablation catheter will be then moved to a contiguous lower or higher site on the predefined circumferential ablation line.

- *PVI confirmation.* Disappearance of PV potentials or dissociated PV potentials in the vein and inability to capture the LA during PV pacing will confirm bidirectional block across the PV circumferential ablation line and PVI.

- *Waiting time.* After a waiting time of 30 min, the PVs will be rechecked in order to confirm the persistence of PVI.

- *Acute PVR.* In case of acute PVR, additional RF ablation will be performed in correspondence of breakthrough signals. The same RF settings of the first PV encirclement will be used.

- *Procedure completion.* The procedure will be terminated after achievement of electrical isolation of all PVs. A trans-thoracic echocardiogram will be performed at the end of the procedure to rule out the presence of pericardial effusion. Protamine will be administered to reverse heparin.

Apart from the RF settings on LA posterior wall (RF power and target LSI) that will be dictated by the study randomization, every other procedure step will be performed according to standard clinical practice. Of note, no particular equipment will be used for the research study rather standard clinical equipment. No additional fluoroscopy time or procedure time will be added to the standard procedure.

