1. SYNOPSIS

Study Title	Radiofrequency Power, Lesion Size Index and Oesophageal Temperature alerts during Atrial Fibrillation ablation: a pilot study	
Internal ref. no. / short title	PiLOT-AF study	
Study Design	Prospective, randomized, single centre observational clinical investigation	
Study Participants	Patients admitted for elective radiofrequency (RF) ablation for paroxysmal or persistent atrial fibrillation (AF)	
Planned Sample Size	80 patients (pilot study)	
Planned Follow-up duration	6 months	
Planned Study Period	15 months	
	Objectives	Outcome Measures
Primary	Assessment of the risk of oesophageal damage associated with radiofrequency (RF) ablation on the left atrial (LA) posterior wall when using different power settings	Luminal oesophageal temperature rises > 39°C during RF application on the LA posterior wall as recorded by an oesophageal temperature probe
Secondary	
Comparison of oesophageal complications with the different RF settings on LA posterior wall
 
Comparison of acute and short-term procedure success using different RF settings on LA posterior wall as marker of lesion transmural and durability
	
Symptoms of oesophageal injury during 6 months follow-up
 
Rate of first-pass pulmonary vein isolation (PVI), rate of acute pulmonary vein reconnection (PVR), total procedure time and RF time of the index ablation procedure
 
AF-free survival during 6 months follow-up

Tertiary	Comparison of rate of procedural complications using the different RF settings	pericardial effusion, TIA/stroke, phrenic nerve injury, pulmonary vein stenosis, open-heart surgery, death

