4. OBJECTIVES AND OUTCOME MEASURES

Objectives	Outcome Measures	Timepoint(s) of evaluation of this outcome measure (if applicable)

Primary Objective
 
To compare the risk of oesophageal damage associated with different RF settings during AF ablation on the LA posterior wall
	
Rate of oesophageal temperature alerts (defined as oesophageal temperature rise > 39°C) during RF ablation on the LA posterior wall
	
Index procedure

Secondary Objectives
 
1. To compare the acute success of the index AF ablation using different RF settings on the LA posterior wall
 
2. To compare the short-term success of the index AF ablation using different RF settings on the LA posterior wall
 
3. To compare the rate of oesophageal injury related to different RF settings on the LA posterior wall during the index AF ablation
	
1. Rate of first-pass PVI, rate of acute PVR related to breakthrough signals on the LA posterior wall, total procedure time and RF ablation time
 
2. Freedom from atrial fibrillation
 
3. Rate of oesophageal symptoms (difficult or painful swallowing, heartburn, acid reflux, sore throat, hoarseness, cough, nausea, vomiting, non-cardiac chest pain)
	
1. Index procedure
 
2. During the follow-up period (6 months)
 
3. During the follow-up period (6 months)

Tertiary objectives
 
To evaluate the rate of complications associated with the different RF settings
	
Pericardial effusion, TIA/stroke, phrenic nerve injury, pulmonary vein stenosis, open-heart surgery, death
	
Index procedure

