5. STUDY DESIGN

The PiLOT-AF study is a prospective single-centre randomized observational study aiming at comparing different RF settings during AF ablation on the LA posterior wall, in terms of oesophageal heating, acute and long-term procedure success and procedural complications.

Patients, age 18-80, scheduled for their first RF ablation because of a history of symptomatic and drug-refractory paroxysmal or persistent atrial fibrillation, will be considered for inclusion in the study.

Potential subjects will initially be approached 4-6 weeks before their ablation procedure, in order to give the patients enough time to consider the information, to ask questions to the Investigator, their GP or other independent parties to decide whether they wish to participate in the study or not.

For those interested in participation, a baseline assessment will be arranged to coincide with their standard pre-admission visit, for informed consent, screening and eligibility assessment and randomization.

All AF ablation procedures will be performed in a standard fashion, under general anaesthesia and with continuous oesophageal temperature monitoring using a sinusoidal multi-sensor oesophageal temperature probe (CIRCAtemp). After LA geometry reconstruction using 3-dimensional electroanatomical mapping EnSite Velocity and a multipolar circular mapping catheter St Jude Medical Optima, a CF ablation catheter Endosense TactiCath through a deflectable sheath St Jude Medical Agilis will be used for PVI. Standardized RF settings will be used during ablation on the LA anterior wall as current practice in our centre. Different RF settings will be used on the LA posterior wall, according to randomization group. Duration of RF delivery on the LA posterior wall will be dictated by achievement of target LSI or oesophageal temperature rise $> 39^{\circ}\text{C}$ during ablation. PVI will be achieved and confirmed after 30 minutes waiting time. In case of acute PV reconnection, ablation at sites of breakthrough signals will be performed in order to achieve durable PVI. The occurrence of acute PV reconnection with sites of breakthrough signals on the LA posterior wall will be recorded for each procedure. The total procedure and RF ablation times will be also collected.

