8. STUDY PROCEDURES

8.1. Recruitment

Potential participants will first be approached 4-6 weeks before the AF procedure. Outpatient clinic letters of patients placed on the waiting list for catheter ablation of AF by the OUH NHS Trust Cardiac Rhythm Management team will be screened by a member of the research team to assess suitability for inclusion in the study. A letter of invitation, a patient information leaflet and a consent form will be given to potential participants at their routine clinic visits or sent by post at the time their procedure date is determined (usually 6 weeks in advance). The letter will contain a reply slip which patients can use to express their interest in the study and request more information if they wish. The participant will be allowed time to consider the information, and the opportunity to ask questions to the Investigator, their GP or other independent parties to decide whether they will participate in the study.

Once patients have had time to consider the information (and discuss with relatives, friends and their GP if they wish), they will be contacted by an investigator who will ask if they wish to discuss the study further. If they wish to take part, they will be approached at their pre-admission visit before the procedure (1-2 weeks before the AF ablation) for a baseline visit including informed consent, screening and eligibility assessment and randomization.

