8.2.3. Randomisation

A block randomization, with blocks of size four, type 1234, will be used to assign each patient to one of the following four treatment arms:

- ✓ Group 1: 20 W RF power and target LSI = 4 on LA posterior wall;
- ✓ Group 2: 40 W RF power and target LSI = 4 on LA posterior wall;
- ✓ Group 3: 20 W RF power and target LSI = 5 on LA posterior wall;
- ✓ Group 4: 40 W RF power and target LSI = 5 on LA posterior wall.

Briefly, the study population will be divided into 4 blocks of 20 patients. Within each block, every patient will be randomly assigned to 1 of the 4 treatment arms by using sealed envelopes. At the end of each block of 20 patients, there will be 5 patients enrolled in each of the 4 treatment arms. At the baseline visit, following consent, the study nurse or doctor will telephone the Research Office and ask the administrator to open a sealed envelope from the current block of 20 and reveal the allocated treatment arm. The treatment will be unblinded to the investigator and blinded to the patient.

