APPENDIX A: STUDY FLOW CHART

APPENDIX B: SCHEDULE OF TIMING OF STUDY APPOINTMENTS AND STUDY PROCEDURES

	Recruit-ment	Baseline visit	Study intervention	Pre-discharge review	Telephone f-up 1	Arrhythmia Clinic visit	Telephone f-up 2
Time since AF ablation	≥ 6 wks	- 1-2 wks	0	+ 1 d	+ 3 mts	3-4 mts	+ 6 mts
Study procedures							
Eligibility assessment	X	X					
Patient's information	X						
Informed consent		X					
Randomisation		X					
Demographics		X					
Medical history		X		X	X	X	X
ECG		X	X	X		X	
AF ablation			X				
Symptom diary instruction				X			
Symptom diary collection					X	X	X

d = day; f-up = follow-up; mts = months; wks = weeks.

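### The arm is disclosed at the baseline visit although nothing before posterior-wall RF needs it, which leaves two avoidable openings for bias: the placement of the ablation line, and exits before ablation

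*Combined protocol and SAP*

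**What the plan says.** **When the arm becomes known.** Section 5 arranges the baseline assessment "for informed consent, screening and eligibility assessment and randomization". Section 8.2.3 states: "At the baseline visit, following consent, the study nurse or doctor will telephone the Research Office", where the administrator opens the envelope and gives the arm. It adds: "The treatment will be unblinded to the investigator and blinded to the patient". Section 8.1 places this visit one to two weeks before the procedure, and the "Time since AF ablation" row of Appendix B agrees.

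**When the arm is first used.** In Section 9 the four groups differ only in power (20 or 40 W) and target LSI (4 or 5) on the posterior wall. Anterior wall, roof and floor have the same settings in every arm. The section closes by saying that all other steps are standard practice.

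**What is decided before that.** Section 9 has the circumferential line laid out in advance on the map, 1-2 cm from the ostia, "with individual adjustments in order to avoid RF delivery in close proximity of the oesophageal probe".

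**What the probe measures.** The Synopsis defines the primary outcome as temperature rises "as recorded by an oesophageal temperature probe". Section 4 words it as "Rate of oesophageal temperature alerts (defined as oesophageal temperature rise" above 39°C).

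**Exits before ablation.** Section 8.7 removes from the analysis anyone withdrawn before the intervention and enrols a replacement, with the reason noted in the CRF. It also lets the investigator discontinue a participant for any reason judged necessary. Section 11.3 says that data already collected on withdrawn patients will be analysed.

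**The concern.** The alert is an objective reading, but how often it occurs plausibly depends on how near the line runs to the oesophagus. An operator who knows that a patient is in a 40 W arm might, without intending to, move the line further from the probe than for a 20 W patient. Part of any difference in alerts would then reflect placement and not power or LSI. The effect could also run the other way and hide a real difference. The plan requires no record of the adjustments or of line-to-probe distance, so a reader could not tell.

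The second opening is selection. Once the arm is known, an unblinded investigator can discontinue a patient before ablation, and Section 8.7 drops and replaces that patient. No section requires a count of all randomised patients by arm, or says which arm the replacement receives.

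Section 11.1 intends the pilot's results to size a main study, so a distorted contrast between arms would carry forward.

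**Working it through.** **1. Order of steps (Sections 8.2.3 and 9)**

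| Step, in listed order | Arm needed? | Arm already disclosed? |
|---|---|---|
| Baseline: consent, eligibility, envelope | No | From here on |
| Anaesthesia and TOE | No | Yes |
| Venous and LA access | No | Yes |
| Temperature probe placed | No | Yes |
| LA geometry | No | Yes |
| Line set on map and adjusted to the probe | No | Yes |
| RF on anterior wall, roof, floor | No | Yes |
| RF on posterior wall | **Yes** | Yes |

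The line is set after disclosure and before first need. Allocation could therefore come after the line without affecting any earlier step.

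**2. The plan's own figure.** Section 11.1 wants 12 patients with primary outcome data in each of four groups, at an alert rate of 55-75%. N = 4 × ceil(12 / rate).
- 60%: 12/0.60 = 20, N = 80. This matches the plan.
- 55%: 12/0.55 = 21.8, so 22, N = 88.
- 75%: 12/0.75 = 16, N = 64.

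The plan does not say which rate it used. Changing the time of disclosure leaves N = 80, or 20 per arm.

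**3. Illustration of size.** The documents give no size for any placement effect, so every shift below is assumed. Also assumed: one yes/no alert per patient, 20 per arm, a 5% level (Section 11.2 names chi-square tests but no level), and no true effect. The 20 W arms have rate p and the 40 W arms p + s. With x_i alerts in arm i and p̂ = Σx_i/80, the statistic is X² = Σ(x_i − 20p̂)² / [20p̂(1 − p̂)] on 3 df, enumerated exactly over all 21⁴ outcomes.

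| p | s | False-positive rate |
|---|---|---|
| 0.65 | 0 | 5.0% |
| 0.65 | −0.05 / +0.05 | 6.3% / 6.4% |
| 0.65 | −0.10 / +0.10 | 10.2% / 11.1% |
| 0.55 | −0.10 / +0.10 | 9.8% / 10.2% |
| 0.75 | −0.10 / +0.10 | 11.1% / 12.6% |

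Masking: if the true rates were 65% (20 W) and 45% (40 W), the same test has 28.9% power. An opposite 10-point shift, giving 65% v 55%, leaves 10.2%.

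**4. What a distance log could show.** Comparing mean line-to-probe distance for 40 v 40 patients (20 W v 40 W), the 95% half-width is t(0.975, 78) × √(2/40) = 1.991 × 0.2236 = 0.445 SD. A two-sample t test reaches 80% power at a difference of 0.634 SD. The log is a coarse check.

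**The case against.** **The discretion is bounded, and the operator cannot be blinded while delivering RF.** This stands in part. The line lies 1-2 cm from the ostia, follows current practice, and after an alert or 60 seconds the catheter moves along that predefined line. These limits reduce the room for a shift but do not exclude one. Section 9 does not say that every adjustment is finished before RF starts, so late disclosure may miss some. Site choice and contact during delivery stay exposed in any case.

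**The operator may not be the person told at baseline.** The documents speak of the investigator and do not say when the operator learns the arm. Equally, nothing keeps it from the operator.

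**The error rates may describe an outcome that the plan does not use.** This stands. Section 11.1 recruits extra patients to cover those with no alert, as if they supplied no primary outcome data. That fits poorly with a yes/no outcome, and Section 4 does not fix the unit. If alerts are counted per patient or per application, the figures in step 3 do not apply.

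**Patients are blinded, so their own withdrawal should not depend on arm.** This is a fair point. It leaves discontinuation by the investigator.

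**A call during the case touches an endpoint.** Total procedure time is a secondary outcome, so the call must not lengthen it.

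A reader might also infer that the gap of one to two weeks is itself harmful. For line placement only the order matters: learning the arm an hour before drawing the line would have the same effect. Nor does detectability turn on whether a shift is small beside the standard error. Placement that depends on arm is confounded with arm, so alert data alone cannot separate the two at any size.

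**Conclusion.** The point holds as an avoidable opportunity for bias, and is worth the sponsor's consideration with moderate confidence. It rests on three things in the documents: the arm is disclosed before the line is set, no earlier step needs it, and the line is adjusted relative to the sensor that records the primary outcome. Section 8.7 adds a window for exclusion after allocation.

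A reader might go further and conclude that placement or exits did differ by arm, or that the trial's false-positive rate is about 10%. The documents support neither. They contain no data on placement or exits, and the size of any bias is unknown. The 10.2% and 11.1% depend on an assumed 10-point shift and an assumed yes/no outcome per patient.

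**What to change.** 1. Keep consent and eligibility at the baseline visit. Make the existing Research Office call on the procedure day, after the line is saved on the map and before posterior-wall RF. A non-operating team member should call in parallel with other work, so that procedure time is not lengthened.
2. Where the mapping system allows, record line-to-probe distance and any later departure from the line, and tabulate both by arm. Section 3.3 says, as background, that the probe can be shown on the map to judge catheter-tip distance; whether line distance can be exported needs checking. The log is worth keeping even if the call cannot move.
3. Report all randomised patients by arm, with reasons for any exit before ablation. Late allocation nearly closes this window, because most such exits would come before the envelope is opened.
4. Identify patients allocated before and after the change.

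**Cost.** Amend Sections 5, 8.1, 8.2.3, 8.7 and 9 and Appendix B. Envelopes, administrator and sample size stay the same. The administrator must be reachable on procedure days. The change comes mid-trial: Appendix C shows that at least 10 cases had been done by the second amendment. The gain is limited to the initial line and exits before the procedure. No change to the line-adjustment rule or RF settings is proposed.

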10. SAFETY REPORTING

10.1. Definition of Serious Adverse Events

A serious adverse event is any untoward medical occurrence that:

- results in death
- is life-threatening
- requires inpatient hospitalisation or prolongation of existing hospitalisation
- congenital anomaly/birth defect
- results in persistent or significant disability/incapacity

Other 'important medical events' may also be considered serious if they jeopardise the participant or require an intervention to prevent one of the above consequences.

NOTE: The term "life-threatening" in the definition of "serious" refers to an event in which the participant was at risk of death at the time of the event; it does not refer to an event which hypothetically might have caused death if it were more severe.

10.2. Reporting Procedures for Serious Adverse Events

A serious adverse event (SAE) occurring to a participant should be reported to the REC that gave a favourable opinion of the study where in the opinion of the Chief Investigator the event was 'related' (resulted from administration of any of the research procedures) and 'unexpected' in relation to those procedures. Reports of related and unexpected SAEs should be submitted within 15 working days of the Chief Investigator becoming aware of the event, using the HRA report of serious adverse event form (see HRA website).

